## 6.2 Visit 1 (Day 1) Enrollment

- Study personnel will review screening study eligibility criteria to ensure unchanged since the initial screening visit.
- Vaginal symptoms such as odor, itching, irritation, and discharge will be reviewed with the participant.
- Vulvovaginal signs such as erythema, edema, excoriation, and discharge, will be documented and graded by severity, as applicable.
- A pelvic examination to include examination of external genitalia will be conducted using a non-lubricated speculum and swabs and samples obtained for analysis of Amsel criteria; KOH and saline microscopy for identification of yeast forms, trichomonas, and clue cells. Instructions for obtaining vaginal swab specimens for these assessments are outlined in the protocol specific MOP.

---

- A clinical determination to confirm BV cure, determined by  $\leq 2$  of 4 Amsel criteria and absence of BV symptoms, are considered eligible for study enrollment. Participants who do not clear BV will be informed that they are no longer eligible. Participants who are BV cured with a secondary VVC infection but appropriate candidates for oral fluconazole treatment can be enrolled. Treatment with oral fluconazole will be per clinic standard of care and provided at no cost to the participant.
- Participants who no longer have BV, will be asked to read and sign the EIC at this time. The EIC form will be signed prior to performing any study procedures.
- Enrollment eligibility criteria will be reviewed with the participant.
- Medical history will be reviewed and updated as appropriate.
- Interim sexual history since the last clinic visit will be collected.
- A urine pregnancy test will be performed on all participants of childbearing potential and must be negative.
- All concomitant medications taken since V0 will be recorded on the appropriate DCF. Previously recorded medications will be updated as appropriate.
- Participants will be registered in Advantage eClinical after being classified as negative for BV and eligible for the study, and randomly assigned to active treatment (TOL-463 Insert) or placebo.
- A targeted physical examination including height and weight will be performed by a qualified study clinician.
- Collect vaginal swabs for Gram staining for Nugent scoring; the BD Max test; and for future analysis, for participants who consented to future use of their specimens. See the protocol-specific MOP for guidance on swab collection.

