3.2.2. Secondary Endpoints

1. Time to BV recurrence.
2. Proportion of participants reporting BV symptoms through the follow-up period.
3. Number of participants satisfied with the study treatment through the follow-up period.
4. The occurrence of AEs considered product-related following initiation of study treatment and through the final study visit.

5. The occurrence of culture confirmed secondary VVC following initiation of study treatment and through the final study visit.

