4. INVESTIGATIONAL PLAN

4.1. Overall Study Design and Plan

This is a Phase II randomized, double-blind, placebo-controlled study screening approximately 600 adult females 18-55 years of age to enroll approximately 250 participants in total (125 per arm) to achieve 200 evaluable participants at the test of cure (TOC) visit. The study is designed to determine the clinical efficacy of an investigational product (IP), TOL-463 Insert, manufactured by Toltec Pharmaceuticals, in suppressing RBV when administered to women who have a history of RBV and have been successfully cleared of their current BV infection using oral metronidazole, 500 mg twice a day for 7 days or another CDC-recommended BV treatment.

Participants who consent to screening will have baseline clinical information collected at Visit 0, screening (Day -15 to -8), (V0). This information will consist of demographics, current vaginal symptoms, medical and sexual history, concomitant medications, and clinical and laboratory findings. Participants will undergo a pelvic examination and have vaginal specimens collected for confirmation of BV and for diagnostic testing for common STIs (*C. trachomatis*, *N. gonorrhoeae*, and *T. vaginalis*). Women with a clinical diagnosis of BV who meet all other screening Inclusion/Exclusion criteria will be treated with oral metronidazole, 500 mg twice a day for 7 days, or another CDC-recommended BV treatment, and scheduled for a Visit 1, enrollment, (V1) in 8 to 15 days. At the enrollment visit, women who test negative for BV, defined as ≤ 2 of 4 Amsel criteria and absence of symptoms of BV (absence of homogenous discharge and odor), will be offered to review and sign the Enrollment consent. Women who consent and qualify will be enrolled and randomized (1:1) to one of two groups (TOL-463 Insert or placebo). IP will be self-administered vaginally, twice-weekly for 12 weeks. Follow-up clinic visits will occur at Visit 2 (V2), Visit 3 (V3), and Visit 4 (V4). For women with cleared BV at enrollment, the primary endpoint will be clinical failure, recurrence of BV by V4.

[figure not shown]
Safety will be measured by participant report, targeted physical examination, and pelvic examination. All AEs will be collected through V4. Safety oversight will be provided by a Data and Safety Monitoring Board (DSMB).

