6.3. Analysis Populations

Safety Population: This analysis population includes all randomized participants who received at least one dose of study treatment. Participants with any evidence of dosing according to the memory aid or study IP packaging return will be included in the Safety population.

Modified Intent-to-Treat (mITT) Population: This analysis population includes all randomized participants who are evaluable (see below). If a participant was enrolled more than once, (participants are allowed to be re-enrolled under PI's discretion for scenarios such as, the first enrollment terminated due to the COVID-19 shelter in place order or became ineligible after enrollment.) only the set of data from the most recent enrollment will be included in the mITT population.

The mITT population will be used as the primary efficacy analysis population.

Per-Protocol (PP) Population: This analysis population includes all randomized participants who are evaluable, complied with the assigned IP (see section 4.4.8), and returned to the study site for the TOC visit within the specified window (Visit 4 [Window: Day 85-91]) or were followed up to their diagnosis of recurrent BV. Participants who violated any inclusion/exclusion criterion at any point during the study or engaged in receptive oral, anal, or vaginal sexual intercourse within 24 hours prior to a study visit will be excluded from the PP population. If a participant was enrolled more than once, (participants are allowed to be re-enrolled under PI's discretion for scenarios such as, the first enrollment terminated due to the COVID-19

shelter in place order or became ineligible after enrollment.) only the set of data from the most recent enrollment will be included in the PP population.

In the unlikely event of an error in randomization or IP administration (i.e., incorrect treatment), participants will be grouped by the treatment they actually received in safety analyses but will be grouped by their intended randomized assignment in efficacy analyses.

Evaluable is defined as follows:

- Negative STI tests taken at baseline (*C. trachomatis*, *N. gonorrhoeae*, or *T. vaginalis*);
- For participants 21 years of age or older, documentation of or self-report of a normal or ASCUS HPV negative Pap test prior to screening, or a Pap smear performed at screening/enrollment with normal result

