9.8. Pelvic Examination Measures

The analyses of Secondary Objective 5 will be conducted in the Safety Population.

The number of subjects, the proportion of subjects with culture confirmed secondary VVC, and the 95% Wilson confidence interval for the proportion of subjects with culture confirmed secondary VVC following the initiation of the study treatment through the follow-up period will be presented overall and by treatment group. In addition, the difference in proportions between the TOL-463 Vaginal Insert arm and the Placebo group and 95% Newcomb confidence intervals (based on the Wilson CI for the individual proportions) will be presented.

The occurrence of culture confirmed secondary VVC following initiation of study treatment and through the final study visit will be summarized in aggregate and by treatment group will be presented in [Table 36](#). [Table 37](#) will present the vulvovaginal signs (edema, erythema, and excoriation) and symptoms (itching, burning, and irritation) and a positive KOH microscopy with identification of yeast forms (hyphae/pseudohyphae) or budding yeasts, which clinician's review of clinical diagnosis of VVC will be based on, as well as the culture confirmed VVC. [Listing 19](#) will present the individual culture confirmed VVC and clinically diagnosed VVC data, including data summarized in [Table 37](#) and the yeast forms identified from the yeast culture.

Additional measurements from the pelvic examinations will be summarized and listed. [Table 38](#) presents genital lesion consistent with active HSV or HPV, Motile Trichomonads present on normal saline wet mount microscopy that indicates Trichomonas vaginalis by treatment group and visit. Individual listing of genital lesion consistent with active HSV or HPV, motile trichomonads and additional abnormal pelvic exam findings will be listed in [Listing 20](#).

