^a Culture confirmed Vulvovaginal Candidiasis at baseline.

Table 23: Summary of Continuous Demographic and Baseline Characteristics by Site - All Enrolled Subjects

Variable	Statistic	University of Alabama (N=X)	University of Pittsburgh (N=X)	University of California (N=X)	All Subjects (N=X)
Age (years)	Mean	xx	xx	xx	xx
	Standard Deviation	xx	xx	xx	xx
	Median	x	x	x	x
	Minimum	x	x	x	x
	Maximum	x	x	x	x
No. of Times Subject Had BV in the Past 12 Months Obtained at Screening Visit	Mean	xx	xx	xx	xx
	Standard Deviation	xx	xx	xx	xx
	Median	x	x	x	x
	Minimum	x	x	x	x
	Maximum	x	x	x	x

Notes: N=Number of enrolled subjects in the specified group. Data from the previous enrollment(s) of a repeat subject are excluded.

Table 24: Summary of Continuous Demographic and Baseline Characteristics by Treatment Group - All Enrolled Subjects

Variable	Statistic	TOL-463 (N=X)	Placebo (N=X)	All Subjects (N=X)
Age (years)	Mean	xx	xx	xx
	Standard Deviation	xx	xx	xx
	Median	x	x	x
	Minimum	x	x	x
	Maximum	x	x	x
No. of Times Subject Had BV in the Past 12 Months Obtained at Screening Visit	Mean	xx	xx	xx
	Standard Deviation	xx	xx	xx
	Median	x	x	x
	Minimum	x	x	x
	Maximum	x	x	x

Notes: N=Number of enrolled subjects in the specified group. Data from the previous enrollment(s) of a repeat subject are excluded.

Table 25: Summary of Subjects with Pre-Existing Medical Conditions by MedDRA System Organ Class and Treatment Group – All Enrolled Subjects

MedDRA System Organ Class	TOL-463 Vaginal Insert (N=X)		Placebo (N=X)		All Subjects (N=X)	
	n	%	n	%	n	%
Any SOC	x	xx	x	xx	x	xx
[SOC 1]	x	xx	x	xx	x	xx
[SOC 2]	x	xx	x	xx	x	xx

Notes: N= Number of enrolled subjects in the specified group; n = Number of subjects reporting medical history within the specified SOC. A subject is only counted once per SOC.

Table 26: Number and Percentage of Subjects with Prior and Concomitant Medications by WHO Drug Classification and Treatment Group – Safety Population

WHO Drug Code Level 1, Anatomic Group	WHO Drug Code Level 2, Therapeutic Subgroup	TOL-463 Vaginal Insert (N=X)		Placebo (N=X)		All Subjects (N=X)	
		n	%	n	%	n	%
Any Level 1 Codes	Any Level 2 Codes	x	xx	x	xx	x	xx
[ATC Level 1 - 1]	Any [ATC 1 - 1]	x	xx	x	xx	x	xx
	[ATC 2 - 1]	x	xx	x	xx	x	xx
	[ATC 2 - 2]	x	xx	x	xx	x	xx
	[ATC 2 - 3]	x	xx	x	xx	x	xx
[ATC Level 1 – 2]	[ATC 2 - 1]	x	xx	x	xx	x	xx
	[ATC 2 - 2]	x	xx	x	xx	x	xx
	[ATC 2 - 3]	x	xx	x	xx	x	xx

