Treatment Group: , Subject ID: , AE Number:											
Comments:											
Treatment Group: , Subject ID: , AE Number:											
Comments:											

Table 36: Occurrence of Culture Confirmed Secondary Vulvovaginal Candidiasis (VVC) Overall and by Treatment Groups – Safety Population

Treatment Group	Number of Subjects N	Number of Subjects with VVC ^a n	Proportion of Subjects with VVC	Proportion of Subjects with VVC 95% CI ^b	Difference in Proportion of Subjects with VVC between Treatment Arms	Difference in Proportion of Subjects with VVC between Treatment Arms 95% CI ^c
TOL-463 Vaginal Insert	x	x	0.xx	0.xx, 0.xx		
Placebo	x	x	0.xx	0.xx, 0.xx	0.xx	0.xx, 0.xx

Notes: The denominator for proportions is based on the number of subjects who used at least one insert in the respective treatment group.

^a The occurrence of culture confirmed secondary VVC following initiation of study treatment and through the final study visit is calculated. Subjects enrolled with concurrent VVC at baseline (visit 1) that can be treated with oral fluconazole is not counted towards n.

^b 95% Wilson confidence interval for the proportion of subjects with VVC.

^c 95% Newcombe confidence interval for difference in proportions between arms.

Table 37: Summary of Proportion of Participants Reporting Vulvovaginal Symptoms and Signs, Yeast Form, and Clinical Diagnosed and Culture Confirmed Vulvovaginal Candidiasis – Safety Population

Symptoms/Signs Severity	TOL-463 Vaginal Insert (N=X)					Placebo (N=X)					All Subjects (N=X)				
	Visit 0	Visit 1	Visit 2	Visit 3	Visit 4	Visit 0	Visit 1	Visit 2	Visit 3	Visit 4	Visit 0	Visit 1	Visit 2	Visit 3	Visit 4
Burning															
n	n	n	n	n	n	n	n	n	n	n	n	n	n	n	n
None	x	x	x	x	x	x	x	x	x	x	x	x	x	x	x
Mild	x	x	x	x	x	x	x	x	x	x	x	x	x	x	x
Moderate	x	x	x	x	x	x	x	x	x	x	x	x	x	x	x
Severe	x	x	x	x	x	x	x	x	x	x	x	x	x	x	x
Irritation															
n	n	n	n	n	n	n	n	n	n	n	n	n	n	n	n
None	x	x	x	x	x	x	x	x	x	x	x	x	x	x	x
Mild	x	x	x	x	x	x	x	x	x	x	x	x	x	x	x
Moderate	x	x	x	x	x	x	x	x	x	x	x	x	x	x	x
Severe	x	x	x	x	x	x	x	x	x	x	x	x	x	x	x
Itching															
n	n	n	n	n	n	n	n	n	n	n	n	n	n	n	n
None	x	x	x	x	x	x	x	x	x	x	x	x	x	x	x
Mild	x	x	x	x	x	x	x	x	x	x	x	x	x	x	x
Moderate	x	x	x	x	x	x	x	x	x	x	x	x	x	x	x
Severe	x	x	x	x	x	x	x	x	x	x	x	x	x	x	x
Edema															
n	n	n	n	n	n	n	n	n	n	n	n	n	n	n	n
Absent	x	x	x	x	x	x	x	x	x	x	x	x	x	x	x
Mild	x	x	x	x	x	x	x	x	x	x	x	x	x	x	x
Moderate	x	x	x	x	x	x	x	x	x	x	x	x	x	x	x
Severe	x	x	x	x	x	x	x	x	x	x	x	x	x	x	x

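### Table 36 footnote a drops women with baseline VVC from the numerator but leaves them in the denominator, so n and N do not match

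*SAP*

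**What the plan says.** Secondary endpoint 5 in SAP 3.2.2 (and Protocol 3.3.2) is "The occurrence of culture confirmed secondary VVC following initiation of study treatment and through the final study visit". SAP 9.8 plans its analysis as a proportion per arm with a Wilson interval and a between-arm difference with a Newcombe interval: "The analyses of Secondary Objective 5 will be conducted in the Safety Population". (SAP 3.1.2 lists only four secondary objectives, so endpoint 5 is evidently meant.) SAP 6.3 defines that population: "This analysis population includes all randomized participants who received at least one dose of study treatment". None of these places, nor Protocol 10.5.3, sets aside women who had VVC at enrollment.

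Such women are in the trial. Protocol 6.2 states: "Participants who are BV cured with a secondary VVC infection but appropriate candidates for oral fluconazole treatment can be enrolled". Women with VVC at Visit 1 who cannot be given fluconazole are excluded by Protocol 5.1.2.2.

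The results shell is SAP Table 36, where n is the number of subjects with VVC. Footnote a says: "Subjects enrolled with concurrent VVC at baseline (visit 1) that can be treated with oral fluconazole is not counted towards n". The general note to the same table says: "The denominator for proportions is based on the number of subjects who used at least one insert in the respective treatment group".

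**The concern.** Footnote a is written about subjects, not episodes. A programmer who follows it will take a woman with VVC at Visit 1, keep her in N because she used an insert, and score her as a non-event even if she has a new culture-confirmed episode at Visit 3. Because women with untreatable VVC at Visit 1 are excluded from the trial, the fluconazole qualifier narrows nothing: every eligible woman with baseline VVC is caught.

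VVC incidence is named in the safety objective, and the product is described as a dual therapy for BV and VVC, so this table will be read. The restriction appears only in a table-shell footnote. It is not in the endpoint or in SAP 9.8, and SAP section 15 says the analyses coincide with the protocol. It also sets two tables against each other: Table 37 shows culture-confirmed VVC by visit in the same population without the restriction, so the woman above would be a Yes at Visit 3 there and a non-event in Table 36.

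**Working it through.** There is no stated figure to reproduce: Table 36 is a blank shell and the documents give no baseline VVC count.

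**Notation, per arm.** N = women who used at least one insert; b = those of them with VVC at Visit 1; f = b/N; x = other women with post-dose culture-confirmed VVC; y = women among the b with a new post-dose culture-confirmed episode.

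**Three quantities.**
- Table 36 as worded: x/N
- Matched at-risk set, women with baseline VVC out of both counts: x/(N − b)
- Whole Safety Population, any new episode: (x + y)/N

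**Against the at-risk set.** x/N = (1 − f) × x/(N − b), so the relative shortfall is exactly f. With 10% among countable women and assumed f:
- f = 5%: 0.95 × 10% = 9.5%
- f = 10%: 0.90 × 10% = 9.0%
- f = 20%: 0.80 × 10% = 8.0%

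In counts, take N = 125 (the planned arm size in SAP 4.1) and an assumed x = 12. Table 36 shows 12/125 = 9.6% (Wilson 5.6% to 16.0%). The at-risk figures are:
- b = 6: 12/119 = 10.1%
- b = 13: 12/112 = 10.7% (6.2% to 17.8%)
- b = 25: 12/100 = 12.0% (7.0% to 19.8%)

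**Against the whole Safety Population.** The shortfall is (x + y)/N − x/N = y/N. With 10% risk in the other women and an assumed risk r in women with baseline VVC, y/N = f × r:

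| f | Table 36 | All Safety, r = 0 | r = 10% | r = 20% |
|---|---|---|---|---|
| 5% | 9.5% | 9.5% | 10.0% | 10.5% |
| 10% | 9.0% | 9.0% | 10.0% | 11.0% |
| 20% | 8.0% | 8.0% | 10.0% | 12.0% |

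The share of all-Safety risk left out is nil at r = 0; 5%, 10% and 20% at r = 10%; and 9.5% (1.0/10.5), 18% (2.0/11.0) and 33% (4.0/12.0) at r = 20%.

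**Between-arm difference** (T = TOL-463, P = placebo). Shown difference = all-Safety difference − (y_T/N_T − y_P/N_P). The last term can have either sign. Two assumed examples:
- Risk 20% in all women of both arms, f = 2% in one arm and 10% in the other: the table shows 0.98 × 20% = 19.6% against 0.90 × 20% = 18.0%, a gap of 1.6 points where the true gap is zero.
- 100 women per arm, x = 10 and 6, y = 0 and 4: the all-Safety figures are 10/100 and 10/100, difference zero; the table shows 10% and 6%, difference 4 points.

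With equal f in both arms, the difference among countable women is multiplied by (1 − f). That is shrinkage relative to the at-risk set only.

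**The case against.** The strongest reply is that the footnote means something harmless. Protocol 6.2 itself applies the word secondary to VVC found at Visit 1, so Table 36 needs a note saying that a Visit 1 case is not a post-treatment event. Footnote a's first sentence restates the full endpoint, and neither SAP 9.8 nor the endpoint definition excludes any woman. Read so, the full denominator is correct and nothing is biased. This is plausible and may be what was intended. It does not rescue the wording, because the sentence bars subjects from n and a programmer would act on that.

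Three further points stand in part.
- The effect may be small. At 125 per arm and 10% risk in women with baseline VVC, f of 5% or 10% hides about 0.6 woman (125 × 0.05 × 0.10) or 1.3 women (125 × 0.10 × 0.10), against a Wilson interval about 10 points wide at 12/125. SAP section 5 also says the study closed early.
- Table 22 (baseline VVC by arm), Table 37 and Listing 19 leave the raw facts visible. They do not correct the estimate and interval in the table that reports the endpoint.
- Counting new episodes is not automatic. *Candida* culture is taken on clinical evidence or at the clinician's discretion, and no clearance culture is scheduled. A positive culture at Visit 2 after VVC at Visit 1 may be the same infection, so the correction has to deal with this.

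**Conclusion.** As worded, footnote a and the denominator note of Table 36 refer to different sets of women, and the footnote departs from the endpoint it is meant to report. In any arm with at least one dosed woman with baseline VVC and at least one counted case, the proportion is below the at-risk proportion by the factor (1 − f). Against whole-Safety incidence the shortfall is y/N. Neither f nor y can be obtained from the documents, so every percentage above is an illustration over an assumed range.

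A reader might infer more than this:
- That the proportion is understated in both arms. An arm with no baseline VVC is unaffected, and against whole-Safety incidence so is an arm with y = 0.
- That the difference is pulled toward zero. This holds only under added assumptions, such as equal baseline shares and the same relative effect in both groups of women; the examples above go the other way.
- That up to a third of the risk is hidden. This needs both a 20% baseline share and a doubled later risk, and the documents support neither.

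The matter is worth correcting because it affects a named secondary safety result at almost no cost. It does not touch the primary analysis, and SAP 9.8 plans estimates with intervals here, not a test.

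**What to change.** Make n and N match before the table is programmed, in one of two ways.

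(a) Keep all Safety women in N and reword footnote a so that only the VVC episode present at Visit 1 is not counted, while any new culture-confirmed episode after the first insert is. State an analysis rule, using data already collected, for telling a new episode from a persisting one. This fits SAP 3.2.2 and 9.8 more closely.

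(b) Remove women with baseline VVC from both n and N, say so in SAP 9.8 as well as in the table, and report these women on a separate line. This could also serve as a sensitivity analysis to (a).

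Under either option, state whether baseline VVC means culture-confirmed, as in the footnotes to Tables 21 and 22, or clinically diagnosed.

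No new data are needed: Tables 22 and 37 and Listing 19 already hold baseline status and culture results by visit. The cost is a reworded footnote plus, under (a), the new-versus-persisting rule, or, under (b), a slightly smaller N.

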APPENDIX 2. FIGURE MOCK-UPS

LIST OF FIGURES

Figure 1: Schematic of Study Design.....	7
Figure 2: CONSORT Flow Diagram	86
Figure 3: Time to Bacterial Vaginosis Recurrence - mITT population	87
Figure 4: Time to Bacterial Vaginosis Recurrence - PP population	87
Figure 5: Number and Severity of Unsolicited Adverse Events by MedDRA System Organ Class - Safety Population.....	88
Figure 6: Number of Unsolicited Adverse Events by MedDRA System Organ Class and Relationship - Safety Population	89

Figure 2: CONSORT Flow Diagram

[figure not shown]
[figure not shown]

Figure 3: Time to Bacterial Vaginosis Recurrence - mITT population

[Implementation notes: 3 curves are for overall and each treatment group. X-axis label: Time (Days) to Bacterial Vaginosis Recurrence, x-axis label: Proportion of Survival.

[figure not shown]
Display, number of subjects at risk table with ticks at day 0, 15, 30, 45, 60, 75, 90 on x-axis, and 95% HW confidence bands of the curves in the plot. Legend names: Treatment arm, All, TOL-463 Vaginal Insert, Placebo. Obtain the estimates in the footnote from the SAS proc lifetest Quartile Estimates output table.]

Notes: The estimate of survival time at which 25% of the overall subjects are expected to have recurrent BV (Proportion of survival equals to 0.75 at y-axis) is **X** days (95% CI: **X - X**), and correspondingly, **X** days (95% CI: **X - X**) for the TOL-463 group and **X** days (95% CI: **X - X**) for the Placebo group.

[figure not shown]
Figure with similar format:

Figure 4: Time to Bacterial Vaginosis Recurrence - PP population

Figure 5: Number and Severity of Unsolicited Adverse Events by MedDRA System Organ Class - Safety Population

Figures will have 3 panels: TOL-463 Vaginal Insert, Placebo, All Subjects

Show footnote if the following scenario exist: Notes: Subjects are excluded from Safety Population if it is unknown whether they received at least one dose, but the adverse events of such subjects are included in the AE listings

Figure 6: Number of Unsolicited Adverse Events by MedDRA System Organ Class and Relationship - Safety Population

Figures will have 3 panels: TOL-463 Vaginal Insert, Placebo, All Subjects

Show footnote if the following scenario exist: Notes: Subjects are excluded from Safety Population if it is unknown whether they received at least one dose, but the adverse events of such subjects are included in the AE listings

